15 SEPTEMBER 2020

PRINCIPAL INVESTIGATOR:

[name] Yale University School of Medicine Department of Internal Medicine Section of Cardiovascular Medicine [name] [contact] [contact] (mobile) [contact] (office)

IND Number: PIND **149901** IND Holder: [name] NCT Number: NCT04415151 Study Phase: 2 **Confidentiality Statement:**

REVISION HISTORY:

Revision #	Version Date
Original	13 April 2020
1	8 May 2020
2	18 May 2020
3	15 June 2020
4	25 June 2020
5	15 September 2020

Synopsis

Primary Objective/Endpoint

• Proportion of subjects alive and not needing any form of mechanical ventilation, high flow oxygen, or ECMO at day 14.

Secondary Objectives/Endpoints

- Clinical improvement as measured by NIAID 8-point ordinal scale (i.e., 1 = death and 8 = Not hospitalized, no limitations on activities) at day 14.
- Clinical status using ordinal scale (days 3 through day 14): The ordinal scale is an assessment of the clinical status at the first assessment of a given study day. The scale is as follows: 1) Death; 2) Hospitalized, on invasive mechanical ventilation or extracorporeal membrane oxygenation (ECMO); 3) Hospitalized, on non-invasive ventilation or high flow oxygen devices; 4) Hospitalized, requiring supplemental oxygen; 5) Hospitalized, not requiring supplemental oxygen requiring ongoing medical care (COVID-19 related or otherwise); 6) Hospitalized, not requiring supplemental oxygen no longer requires ongoing medical care; 7) Not hospitalized, limitation on activities and/or requiring home oxygen; 8) Not hospitalized, no limitations on activities.* For patients on chronic home O2 supplementation, supplemental O2 is defined as >= home O2 requirement. ** Use of NIV for chronic conditions [e.g. Obstructive sleep apnea (OSA)] is not applicable
- Time to recovery [Time Frame: Day 1 through Day 14] (Day of recovery is defined as the first day on which the subject satisfies one of the following three categories from the ordinal scale: 1) Hospitalized, not requiring supplemental oxygen - no longer requires ongoing medical care; 2) Not hospitalized, limitation on activities and/or requiring home oxygen; 3) Not hospitalized, no limitations on activities).
- Time to clinical improvement (defined as a 2-point increase on the ordinal scale)".
- Clinical status on ordinal scale at day 30, 60, and 90
- Mortality rate at day 30, 60, 90
- Proportion of patients requiring ICU admission and mechanical ventilatory support
- Change from baseline in inflammatory parameters (e.g., hsCRP, procalcitonin, ferritin, D-dimers, LDH, fibrinogen, PT/PTT)
- Change from baseline in cytokines (e.g. IL-1, IL-2, IL-6, IL-8, TNF-α, IL-17A, IL-17F, IP-10, CCL5), as available
- Safety as assessed by reporting of adverse events, changes in clinical laboratory parameters (e.g., hemoglobin, hepatic transaminases, serum creatinine, bilirubin, and evidence of secondary infections)
- Intervention with additional immunomodulatory agent (i.e. IL-6 targeting therapy)
- Change in SARS-CoV-2 viral titers during intervention

Study Duration

• 10 months

Study Design

Randomized, double-blinded, placebo-controlled phase 2B study

Number of Study Sites

1 – Yale New Haven Health System

Study Population

Male and female subjects age 18 to 99 hospitalized with moderate SARS-CoV-2 infection

Number of Participants

60

Primary Outcome Variables

• Proportion of subjects alive and not needing any form of mechanical ventilation, high flow oxygen, or ECMO at day 14.

Secondary and Exploratory Outcome Variables (if applicable)

- Clinical improvement as measured by NIAID 8-point ordinal scale (i.e., 1 = death and 8 = Not hospitalized, no limitations on activities) at day 14.
- Clinical status using ordinal scale (days 3 through day 14): The ordinal scale is an assessment of the clinical status at the first assessment of a given study day. The scale is as follows: 1) Death; 2) Hospitalized, on invasive mechanical ventilation or extracorporeal membrane oxygenation (ECMO); 3) Hospitalized, on non-invasive ventilation or high flow oxygen devices; 4) Hospitalized, requiring supplemental oxygen; 5) Hospitalized, not requiring supplemental oxygen requiring ongoing medical care (COVID-19 related or otherwise); 6) Hospitalized, not requiring supplemental oxygen no longer requires ongoing medical care; 7) Not hospitalized, limitation on activities and/or requiring home oxygen; 8) Not hospitalized, no limitations on activities.* For patients on chronic home O2 supplementation, supplemental O2 is defined as >= home O2 requirement. ** Use of NIV for chronic conditions [e.g. Obstructive sleep apnea (OSA)] is not applicable
- Time to recovery [Time Frame: Day 1 through Day 14] (Day of recovery is defined as the first day on which the subject satisfies one of the following three categories from the ordinal scale: 1) Hospitalized, not requiring supplemental oxygen no longer requires ongoing medical care; 2) Not hospitalized, limitation on activities and/or requiring home oxygen; 3) Not hospitalized, no limitations on activities).
- Time to clinical improvement (defined as a 2-point increase on the ordinal scale)".
- Clinical status on ordinal scale at day 30, 60, and 90
- Mortality rate at day 30, 60, 90
- Proportion of patients requiring ICU admission and mechanical ventilatory support
- Change from baseline in inflammatory parameters (e.g., hsCRP, procalcitonin, ferritin, D-dimers, LDH, fibrinogen, PT/PTT)

- Change from baseline in cytokines (e.g. IL-1, IL-2, IL-6, IL-8, TNF-α, IL-17A, IL-17F, IP-10, CCL5), as available
- Safety as assessed by reporting of adverse events, changes in clinical laboratory parameters (e.g., hemoglobin, hepatic transaminases, serum creatinine, bilirubin, and evidence of secondary infections)
- Intervention with additional immunomodulatory agent (i.e. IL-6 targeting therapy)
- Change in SARS-CoV-2 viral titers during intervention

1 Introduction

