5.3.2 Eligibility Criteria/Vulnerable Populations

Inclusion Criteria:

Participants are eligible to be included in the study only if all of the following criteria apply:

Age and Sex:

Male or female participants between the ages of 18 and 99 years, inclusive, at screening. Refer to **Appendix 3** for contraceptive guidance for participants.

Type of Participant and Disease Characteristics:

- 1. Participants who are willing and able to comply with all scheduled visits, treatment plan, laboratory tests, lifestyle considerations, and other study procedures.
- 2. Participants with laboratory-confirmed novel coronavirus (SARS-CoV-2) infection as determined by polymerase chain reaction (PCR) or other commercially available or public health assay prior to Day 1.

- Participants with evidence of pneumonia assessed by radiographic imaging (chest x-ray or chest CT scan) AND Requiring ≥ 3L O2 OR ≥ 2L O2 and hsCRP > 70 mg/L
- 4. Participants who are hospitalized and receiving supportive care for COVID-19.

Informed Consent:

Participant (or legally authorized representative/surrogate) capable of giving signed informed consent.

Exclusion Criteria:

Participants are excluded from the study if any of the following criteria apply:

Medical Conditions:

- 1. Require mechanical ventilation or ECMO on Day 1 at the time of randomization.
- 2. Have current, or history of, venous thromboembolism (deep vein thrombosis or pulmonary embolism).
- 3. Have a personal or first-degree family history of blood clotting disorders.
- 4. Participants who are immunocompromised, with known immunodeficiencies, or taking potent immunosuppressive agents (eg, azathioprine, cyclosporine).
- 5. Participants with any current malignancy or lymphoproliferative disorders that requires active treatment
- 6. Females of child bearing potential who are pregnant or breastfeeding
- 7. Other medical or psychiatric condition including recent (within the past year) or active suicidal ideation/behavior or laboratory abnormality that may increase the risk associated with study participation or, in the investigator's judgment, make the participant inappropriate for the study.
- 8. Anticipated survival < 72 hours as assessed by the Investigator.

Infection History:

- Suspected or known active systemic bacterial, fungal, or viral infections (with the exception of COVID-19) including but not limited to:
 - Secondary bacterial pneumonia;
 - Active herpes zoster infection;

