6.5.4 Safety

Included as secondary objective.

All safety analyses will be performed on the Safety Analysis Set. All safety data will be summarized descriptively through appropriate data tabulations, descriptive statistics, categorical summaries, and graphical presentations.

Change from baseline in inflammatory parameters or cytokines will be summarized by descriptive statistics (N, mean, standard error of the mean, minimum, 1st, 2nd (ie, median) and 3rd quartiles and maximum).

Safety Analysis Set (SAF) is defined as all participants randomly assigned to study intervention and who take at least 1 dose of study intervention. Participants will be analyzed according to the intervention they actually received. All safety analysis will be based on SAF.

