### 2.2.1. Estimands

The estimand with treatment policy strategy will be utilized. All observed data (regardless of whether an intercurrent event occurs) will be included in the analysis. It includes the following 4 attributes:

- Population: Participants with COVID-19 pneumonia who meet all inclusion/exclusion criteria. The analysis will consider all observed data without employing any imputation for missing data;
- Variable: Yes or No for the occurrence of the event for categorical endpoints (including Binary endpoints), change from baseline for continuous endpoints and time to event for time to event endpoints.
- Intercurrent event(s): discontinuation of study intervention due to any reason or receiving rescue therapy.
- Population level summary: Proportion for categorical endpoints (including binary endpoints), mean for continuous endpoints and median time to event for time to event endpoints.

[figure not shown]

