**5.2.2. Analyses for Continuous Endpoints**

Continuous endpoints will be analyzed using the Estimand with treatment policy strategy specified in Section 2.2.1.

The data for each continuous endpoint will be summarized by treatment group and by time point in tables containing descriptive statistics (N [which is the number of participants evaluable for the endpoint at the time point], mean, standard deviation, standard error of the mean, minimum, 1st, 2nd (i.e., median) and 3rd quartiles and maximum) for actual and change from baseline values for those endpoints measured at baseline. In case when N=1 (i.e., only one participant is available/evaluable for summary), standard deviation and standard error will be reported as “NA” (not applicable) while the remaining statistical parameters will

have the same value as the mean. For selected endpoints, mean (+/-SD) over time by treatment group will be plotted.

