#### **7. INTERIM ANALYSIS**

No interim analysis will be performed. Safety data will be reviewed by a Yale DSMB.

The first safety review was conducted after randomization of 24 subjects and there was no further review as additional patients were not enrolled.

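### Biomarker results are reported by arm as unadjusted change from baseline; with 24 patients, a supportive baseline-adjusted estimate would reduce the effect of chance baseline differences

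*Protocol*

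**What the plan says.** The protocol synopsis lists "Change from baseline in inflammatory parameters (e.g., hsCRP, procalcitonin, ferritin, D-dimers, LDH, fibrinogen, PT/PTT" among the secondary endpoints, with separate entries for cytokines and viral titre. The analysis is set elsewhere.

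- Protocol 6.5.4: "Change from baseline in inflammatory parameters or cytokines will be summarized by descriptive statistics (N, mean, standard error of the mean, minimum", then quartiles and maximum.
- SAP 5.2.2: "The data for each continuous endpoint will be summarized by treatment group and by time point in tables containing descriptive statistics". These cover "actual and change from baseline values for those endpoints measured at baseline". SAP 2.2 classes viral titre as continuous, so it follows the same rule.
- SAP 2.2.1 gives the population-level summary as the "mean for continuous endpoints and median time to event for time to event endpoints".
- SAP 6.4.1 summarises baseline PT/PTT, fibrinogen, D-dimer, hs-CRP, ferritin, procalcitonin and LDH by arm. It lists no cytokine and no viral titre.
- SAP 2.1 and 5.1 rule out hypothesis tests between arms.
- SAP 7: "The first safety review was conducted after randomization of 24 subjects", and no patient was enrolled after that.
- Allocation is 1:1 in Protocol 5.1 and 6.4.2 but 2:1 in SAP 2.3. The documents do not state the actual arm sizes.

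Neither document fits a model to these endpoints or uses baseline as a covariate.

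**The concern.** Change from baseline depends on the starting value. Unless baseline and follow-up are strongly related, the arm that happens to start higher tends to fall further without any drug effect. Two small arms can easily start apart, and Protocol 6.1.5 and 6.1.7 describe no stratification that would limit this.

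The plan makes no formal comparison, but readers will set the two columns side by side. Protocol 6.2.4 says that the research samples serve to understand responses to tofacitinib relative to SOC, and the dose argument in Protocol Appendix 4 rests on predicted IL-6 inhibition and on observed suppression of IP-10 and CRP. At stake is how a reader interprets a difference in mean fall in hsCRP, ferritin, a cytokine or viral titre: part of it may reflect where the arms began, and it may be less precise than the collected data allow.

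**Working it through.** **No stated figure to reproduce.** The documents give no sample size, SD or correlation for the biomarkers. The only power statement (Protocol 6.4.2, 73%) concerns the primary binary endpoint and is not affected here.

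**Inputs.** From the documents: 24 randomised (SAP 7); 1:1 gives 12/12, 2:1 gives 16/8; 30/30 as planned in the protocol. Assumed: correlation r between baseline and follow-up from 0.2 to 0.8, and ratio k = follow-up SD / baseline SD of 0.5, 1 or 0.9/0.7 = 1.29. Values are taken as normal on the scale analysed.

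**Step 1: chance baseline difference.** In baseline SD units, SE = √(1/n₁ + 1/n₂), and P(|difference| > 0.5) = 2 × [1 − Φ(0.5/SE)].

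| Arms | SE | 95% range | P(above 0.5 SD) |
|---|---|---|---|
| 12/12 | 0.408 | ±0.80 | 22% |
| 16/8 | 0.433 | ±0.85 | 25% |
| 30/30 | 0.258 | ±0.51 | 5% |

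**Step 2: share carried into the difference in mean change.** With no drug effect and a baseline difference d, the expected difference in mean change is −(1 − r·k)·d.

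| r | k = 0.5 | k = 1 | k = 1.29 |
|---|---|---|---|
| 0.2 | 0.90 | 0.80 | 0.74 |
| 0.4 | 0.80 | 0.60 | 0.49 |
| 0.6 | 0.70 | 0.40 | 0.23 |
| 0.8 | 0.60 | 0.20 | −0.03 |

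For example, with k = 1, d = 0.5 SD and r = 0.4, the arm that starts higher shows a larger mean fall by 0.60 × 0.5 = 0.30 SD. The share is complete only at r = 0.

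**Step 3: is there bias?** In 200,000 simulated trials at 12/12 with r = 0.5 and k = 1, the average difference in change was 0.00. Its slope on the baseline difference was −0.50, as the formula gives; for ANCOVA the slope was 0.00. The effect is conditional on the imbalance that occurs and averages to zero over randomisations.

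**Step 4: precision.** Apart from the common factor (1/n₁ + 1/n₂) and in units of the baseline variance:

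- difference in raw change: 1 + k² − 2rk
- ANCOVA difference: k²(1 − r²) × [1 + 1/(N − 4)], where the bracket is the cost of estimating the slope; at N = 24 it is 1 + 1/20 = 1.05

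The bracket depends on the total N, so the percentages below hold for 12/12 and 16/8 alike. For r = 0.2 and k = 1: raw 1.60, ANCOVA 0.96 × 1.05 = 1.008, ratio 0.63, a 37% cut.

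| r | Change in variance, k = 1 | Change in variance, k = 1.29 |
|---|---|---|
| 0.2 | −37% | −22% |
| 0.4 | −26% | −10% |
| 0.6 | −16% | 0% |
| 0.8 | −5% | +5% |

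If the follow-up SD is half the baseline SD (k = 0.5), as could happen if markers normalise, the cut is 74% to 79%.

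**Step 5: smaller cells.** Values are analysed as observed (SAP 5.3), so N falls over time. With 14 contributing patients, chosen for illustration, the bracket is 1 + 1/10 = 1.10. At k = 1 and r = 0.8 the ratio is then 0.90 × 1.10 = 0.99, almost no gain.

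**The case against.** The strongest reply is that SAP version 2.0 deliberately stops at description after early termination. Each arm's mean change is a valid description of that arm, and the problem arises only when a reader makes a comparison that the SAP does not make. This stands, and it limits the point to a supportive addition. It does not remove the point: results are tabulated by randomised arm, and Protocol 6.2.4 states a comparative purpose for the samples.

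A reader might infer that the baseline is used only for subtraction and that any imbalance stays hidden. The documents do not support that. SAP 6.4.1 tabulates seven baseline inflammatory markers by arm, and SAP 5.2.2 tabulates actual values with median and quartiles beside change. Displaying an imbalance does not remove it, however. A baseline summary of all patients also need not describe those still contributing at a later time point, because daily assessments are made while patients are hospitalised and nothing is imputed.

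A reader might also infer that the entry rule "Requiring ≥ 3L O2 OR ≥ 2L O2 and hsCRP > 70 mg/L" makes the arms differ. It allows entry hsCRP to vary, but it applies equally to both arms and creates no imbalance between them.

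Two further objections stand. The size of the gain rests entirely on assumed r and k and can be slightly negative. And SAP 5.2.2 itself provides for cells with N = 1, where no ANCOVA can be fitted, so adjustment at every time point is not feasible.

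**Conclusion.** The point holds in a limited form. The plan contains no baseline-adjusted estimate for the biomarkers. With 24 patients, a chance baseline difference above 0.5 SD has a probability of about 22% (12/12) to 25% (16/8), against 5% at the planned 30/30, and a share 1 − r·k of it enters a side-by-side reading of mean change with opposite sign.

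It would be tempting to say that the imbalance passes in full into the result, or that the planned summaries are biased. Neither follows: the share is full only at r = 0, it nearly vanishes at r = 0.8 with k = 1.29, and the average over randomisations is zero. The cost is conditional imbalance and lost precision.

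Adjustment would cut the variance of the arm difference by about 37% to 5% for r from 0.2 to 0.8 with equal SDs, and by 22% down to a 5% loss with k = 1.29. These figures assume normality and all 24 patients contributing, and they compare the two methods on the same scale. SAP 5.2.2 specifies no log transformation, so they do not describe the planned raw-scale tables exactly where markers are skewed.

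**What to change.** In SAP 5.2.2:

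1. Keep the raw tables of actual and change values as planned.
2. Add, labelled supportive and exploratory and without a test, the baseline-adjusted mean per arm with 95% CI. Take it from an ANCOVA of the log value on arm and log baseline, evaluated at the common baseline mean. State a rule for values below the assay limit, which the log requires.
3. Restrict it to the main scheduled time points, for example Day 7 and Day 14/end of treatment, and to markers that reach a pre-stated minimum N per arm.
4. Beside each change, show the baseline of the patients who contribute to it. Include cytokines and viral titre, which SAP 6.4.1 does not list.
5. Reconcile the 1:1 and 2:1 allocation ratios and state the actual arm sizes.

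This needs no new data and, being free of tests, does not conflict with SAP 2.1 or 5.1. The cost is a few lines of SAP text and extra columns for selected tables. The downside is a simple model fitted in small arms, with negligible gain or a slight loss of precision if the correlation is high.

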1.1 Introductory Statement

This document is a protocol for a human research study. The purpose of this protocol is to ensure that this study is to be conducted according to ICH GCP guidelines, and according to CFR 21 Part 312, other applicable government regulations and Institutional research policies and procedures.

2 Background

2.2 Background/prevalence of research topic

Patients with SARS-CoV-2 may manifest cytokine release syndrome (CRS), associated with systemic inflammation, hemodynamic instability, and multiple organ failure. CRS is among the key reasons for SARS-CoV-2 related mortality.

Multiple cytokines, including IL-6, are involved in CRS. Indeed, the IL-6 receptor antibody tocilizumab is FDA approved for the treatment of Chimeric Antigen Receptor T (CART) Cell-Induced Severe or Life-Threatening CRS. Anti-IL-6 antibody treatment is being used in some cases of SARS-CoV-2, and treatment with tocilizumab is standard of care at YNHH as of April 4, 2020. However, the only data to support the use of tocilizumab is a 21-patient retrospective case series from China.⁸ A therapy targeting multiple cytokines, including IL-6, may prove effective in SARS-CoV-2 -induced CRS.

JAK-STAT signaling is a pro-inflammatory pathway that is activated downstream of multiple cytokines, including IL-6. JAK inhibitors (JAKi) are small molecule inhibitors of one or more of the Janus kinase (JAK) family of enzymes and are used to treat hematological and inflammatory diseases. Over 50 cytokines signal through the JAK-STAT pathway, and hence JAK inhibitors have the potential to suppress the activity of multiple cytokines, including IL-2, IL-4, IL-6, IL-15, interferon gamma, and IL-21.

Oral tofacitinib was approved by the FDA in 2012 for the treatment of moderately to severely active RA who have had an inadequate response to, or who are intolerant of, methotrexate. It has recently been approved for the treatment of psoriatic arthritis (PsA) and ulcerative colitis (UC). Its use is being studied in other inflammatory diseases, including juvenile idiopathic arthritis. The recommended dose of tofacitinib is 5 mg twice daily for RA and PsA and up to 10 mg twice daily for UC. The following table presents the risks as summarized in the original package insert for XELJANZ for RA. The risk profile has not changed significantly following studies of tofacitinib in other diseases.

Tofacitinib is an orally administered, synthetic small molecule that selectively inhibits the JAK family of kinases (preferentially JAK1/JAK3) and is currently FDA-approved for the treatment of rheumatoid arthritis (RA), psoriatic arthritis (PsA), graft vs. host disease (GVHD) and ulcerative colitis (UC). Unlike targeted biologic therapies, which are directed at extracellular

targets such as individual soluble cytokines (e.g. TNF- α), cytokine receptors (IL-1R, IL-6R) or other cell surface receptors (CD20, CD80, and CD86), tofacitinib works intracellularly² and has been developed to target a number of cytokines known to have a role in inflammatory diseases (Figure 1).

Figure 1. Tofacitinib Mechanisms of Action - Biological Significance of Signaling Through Different JAK Combinations

Abbreviations: IL=interleukin; IFN=interferon; EPO=erythropoietin; TPO=thrombopoietin; GM-CSF= granulocyte macrophage colony-stimulating factor; CSF=colony-stimulating factor; JAK= Janus-Kinase; TYK2= tyrosine kinase 2; Th17=T-helper phenotype. Cytokine signaling is mediated by specific JAK and STAT combinations due to preferential binding to the intracellular domains of the individual cytokine receptor chains. For example, JAK3 only associates with the γ - common chain and therefore only mediates IL-2, -4, -7, -9, - 15, and -21 signaling, whereas JAK1 plays a broader role in cytokine signaling. Adapted from reference¹⁰.

Dose Rationale

The safety and clinical pharmacology of tofacitinib has been very well characterized. The pharmacodynamics (PD) of the tofacitinib, in terms of cytokine inhibition and biomarkers of pharmacologic activity, have been characterized in *in vitro* studies, animal models, and *in vivo* clinical studies. These data indicate rapid onset, followed by sustained pharmacologic activity over the dosing period. At a 10 mg BID dose, approximately 80% suppression of IL-6 may be expected, in addition to substantial inhibition of multiple other pro-inflammatory cytokines, such as IFN_{γ}, IL-15, IL-21, and IL-27, supporting the use of tofacitinib 10 mg BID for prevention of overexpression of cytokines in SARS-CoV-2 infected patients. Given the high mortality of COVID-19 complicated by ARDS, and the overall case mortality rate in COVID-19 patients, a tofacitinib dose of 10 mg immediate release formulation BID is

expected to provide maximal cytokine suppression while maintaining an overall positive benefit-risk profile.

If concomitant administration of a strong inhibitor of CYP3A4 (eg, ketoconazole, clarithromycin, ritonavir/lopinavir) or a moderate inhibitor of CYP3A4 that is also a strong inhibitor of CYP2C19 (eg, phenytoin, fluvoxamine, fluconazole) cannot be avoided, a reduced dose of tofacitinib 5 mg BID is recommended and will provide similar target coverage.

Because patients are likely to be discharged from the hospital soon after returning to clinical baseline, we will continue to administer tofacitinib 5 mg BID for a total duration of treatment of 14 days in order to prevent rebound of CRS that could theoretically occur with abrupt cessation of immunomodulatory therapy. In these cases, patients will be discharged home with a pill bottle labeled as investigational drug containing the appropriate number of pills (either tofacitinib or placebo).

3 Rationale/Significance

